5.1.7.2 Technical Computational Details for the Analysis of the Secondary Endpoints

- 1) Baseline for the continuous secondary endpoints of the subjects receiving tolvaptan in the Optional Tolvaptan Treatment Component is the last evaluation prior to the first dose at each cycle in the Optional Tolvaptan Treatment Component. This applies to ALT, AST and BT.
- 2) Baseline for the continuous secondary endpoints except QoL and serum sodium of the subjects participating in the Core Safety Follow-up Component is the last evaluations from the previous trial, if the last evaluation was done in previous trials within one month of this trial starts. If more than one month passes between trials, the baseline will be the evaluations at the baseline visit of this trial.
The baseline for QoL and serum sodium of the subjects in the Core Safety Follow-up Component is the evaluations at the baseline visit.
- 3) The QoL assessment includes the PedsQL Generic Core Scale (QoL GCS) and PedsQL Multidimensional Fatigue Scale (QoL MFS). For the QoL GCS, the change from baseline in QoL GCS total score, physical health summary score, and psychosocial health summary score will be analyzed using the descriptive statistics. For the QoL MFS, the QoL MFS total score will be analyzed using the descriptive statistics.
- 4) The QoL GCS scale consists of 23 items encompassing physical, emotional, social, and school domains.
For ease of interpretability, items are reversed scored and linearly transformed to a 0-100 scale, so that higher scores indicate better HRQOL (Health-Related Quality of Life).

To reverse score, transform the 0-4 scale items to 0-100 as follows: 0 = 100, 1 = 75, 2 = 50, 3 = 25, 4 = 0.

To create scale scores, the mean is computed as the sum of the items divided by the number of items answered (this accounts for missing data). If more than 50% of the items in the scale are missing, the scale scores should not be computed. If 50% or more items are completed, then impute missing scores by the mean of the completed items in a scale.

To create the Psychosocial Health Summary Score, the mean is computed as the sum of the items divided by the number of items answered in the Emotional, Social, and School Functioning Scales. The Physical Health Summary Score is the same as the Physical Functioning Scale Score.

To create the total scale score, the mean is computed as the sum of all the items divided by the number of items answered on all the scales.

Child self-reported data for subjects with age ≥ 5 years will be used in the analysis, while for subjects with age < 4 years, parent-reported data will be used.

- 5) The QoL MFS scale consists of 18 items in 3 subscales: general fatigue, sleep/rest fatigue, and cognitive fatigue.

Items are reversed scored and linearly transformed to a 0-100 scale as follows: 0 = 100, 1 = 75, 2 = 50, 3 = 25, 4 = 0.

To create scale scores for each dimension, the mean is computed as the sum of the items divided by the number of items answered.

The total QoL MFS score will be calculated by summing up all the items divided by the number of items answered on all the scales.

If more than 50% of the items in the scale are missing, the scale scores should not be computed. If 50% or more items are completed, then impute missing scores by the mean of the completed items in a scale.

Child self-reported data for subjects with age ≥ 5 years will be used in the analysis, while for subjects with age < 4 years, parent-reported data will be used.

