5.1 Efficacy Analysis

Due to the early termination status, not all planned analyses will be provided due to lack of data. For an example, no subject received optional Tolvaptan treatment, the efficacy analyses specified in the SAP will not be applied to Optional Tolvaptan Treatment Component.

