5.1.2 Handling of Missing Data

The primary dataset for efficacy analyses will be the observed cases (OC) dataset. The OC dataset will consist of the actual observations recorded at each visit so that no imputation of missing values will be made.

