5.1.3 Baseline Characteristics and Baseline Comparability

Demographic characteristics and medical history at baseline will be summarized by descriptive statistics, e.g., proportion, mean, median, standard deviation(SD), minimum and maximum values.

Baseline characteristics by age categories (≥ 4 weeks to < 4 years, ≥ 4 years to < 8 years, ≥ 8 years to < 12 years, ≥ 12 years to < 18 years) will also be provided. Baseline characteristics by underlying etiology (heart failure, hepatocellular disease, syndrome of inappropriate antidiuretic hormone secretion (SIADH) or other diseases) will be provided as well.

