5.1.7 Secondary Outcome Analysis

5.1.7.1 Analyses of Secondary Outcome Variables

The secondary endpoints for all subjects receiving tolvaptan in the Optional Tolvaptan Treatment Component of the trial include the following:

- Percentage of subjects who require rescue therapy while on tolvaptan
- Percentage of subjects who have recurrence of hyponatremia while on tolvaptan

- Percentage of subjects requiring continuation of tolvaptan following 30 days of treatment
- Percentage of subjects with overly rapid correction in serum sodium (≥ 12 mEq/L [mmol/L]) in 24 hours after the first dose at introduction or reintroduction of tolvaptan
- Changes from baseline in ALT, AST, BT and creatinine for subjects on tolvaptan

The secondary endpoints for subjects participating in the Core Safety Follow-up Component of the trial include:

- Frequency of AE reports
- Change from baseline in QoL assessments
- Change from baseline in growth percentiles by visit for body height and weight
- Tanner Staging progression score (at 6 months)

All secondary endpoints will be summarized using descriptive statistics.

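### SAP 5.1.7.2 assigns no PedsQL reporter to children aged 4 to under 5 years, on either scale

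*SAP*

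**What the plan says.** SAP 5.1.7.2 closes item 4 (Generic Core Scale) and item 5 (Multidimensional Fatigue Scale) with the same sentence. It opens "Child self-reported data for subjects with age ≥ 5 years" and continues "will be used in the analysis, while for subjects with age < 4 years, parent-reported data will be used". No third age range follows in either item.

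The rule feeds change from baseline in quality of life. SAP 5.1.7.1 places that endpoint in the list that opens "The secondary endpoints for subjects participating in the Core Safety Follow-up Component of the trial include". For the Generic Core Scale, item 3 of 5.1.7.2 says that "the change from baseline in QoL GCS total score, physical health summary score, and psychosocial health summary score will be analyzed"; for the Fatigue Scale it names the total score. On the reference point, item 2 says: "The baseline for QoL and serum sodium of the subjects in the Core Safety Follow-up Component is the evaluations at the baseline visit".

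Protocol 3.7.4.2 describes both instruments as suitable from 2 years of age and lists four bands: 2–4, 5–7, 8–12 and 13–18 years. It lets the subject or the parent or caregiver complete the form, depending on age, and gives no cut-off.

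**The concern.** A reporter rule should cover every age that the instrument covers. This one leaves a band between its two limits. A programmer who codes the two conditions literally gets no record for a child aged 4 to under 5, and one who notices the hole has to settle it without an instruction from the plan.

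At stake is whether these children contribute to the quality-of-life summaries for the core component. The gap is in a stated rule with specific limits, so it differs from a detail merely left to later programming notes.

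**Working it through.** No sample size, power or error rate is involved. The check is whether the two stated ranges cover all ages.

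**Inputs**
- Self-report: age ≥ 5 years (SAP 5.1.7.2, items 4 and 5).
- Parent report: age < 4 years (same sentences).
- Instrument bands: 2–4, 5–7, 8–12, 13–18 years (protocol 3.7.4.2).
- Summarised scores (SAP 5.1.7.2, item 3): Generic Core Scale total, physical health summary and psychosocial health summary; Fatigue Scale total.

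**Step 1, coverage.** The ranges {age < 4} and {age ≥ 5} together omit exactly 4 ≤ age < 5. The width is 5 − 4 = 1 year. In completed years, only age 4 is unassigned. Both items use the same limits, so the gap is the same for both scales.

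**Step 2, scores affected.** 3 (Generic Core Scale) + 1 (Fatigue Scale) = 4, which is every quality-of-life score that item 3 names.

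**Step 3, whether another section fills the gap.** Protocol 3.7.4.2 puts a 4-year-old in the Toddler band (2–4 years) and starts the next band at 5, so its bands have no hole in completed years. It does not say who reports on the Toddler form, so it points to a limit of under 5 without stating one. SAP 5.1.2 says "The OC dataset will consist of the actual observations recorded at each visit so that no imputation of missing values will be made"; that governs missing values, not the choice of respondent.

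**Step 4, whether such children can be in the analysis.** Protocol 3.4.3 sets no exclusion criteria for the core component. SAP 5.1.3 plans "Baseline characteristics by age categories (≥ 4 weeks to < 4 years, ≥ 4 years to < 8 years", so its second category begins at 4 years. Core inclusion criterion 2 (protocol 3.4.2) asks for the subject's own assent, but protocol 3.4.1 qualifies assent as being obtained where appropriate, and the SAP also has a category below 4 years. The assent criterion therefore does not clearly keep 4-year-olds out.

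**Step 5, the rule with the limit moved.** {age < 5} and {age ≥ 5} cover all ages with no overlap, and the split falls where the protocol's bands change from 2–4 to 5–7.

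**The case against.** The strongest reply is that the sentence is silent about age 4 and does not exclude it. Quality of life is listed among the efficacy variables in protocol 3.5.2.1, the efficacy data are observed cases, and a completed form would ordinarily be analysed whoever filled it in. That is fair as to intent: a reader might infer that the SAP deliberately drops 4-year-olds, and nothing in it says so. What survives is narrower. The written conditions pick out no report for this age, and no other section supplies one.

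A reader might also infer that the source would be picked after both reports had been seen. The documents do not support that. Protocol 3.7.4.2 reads most naturally as one respondent per child, settled at collection, and no section requires both forms.

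A third reply is that the practical effect is close to nil. The endpoint is descriptive, form availability may be limited for some ages and languages (protocol 3.7.4.2), and SAP 5.1 says that "not all planned analyses will be provided due to lack of data". This stands and caps the severity. It does not make the point moot: the example in SAP 5.1 of what is dropped is the optional-treatment efficacy analysis, and core quality of life is not named.

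**Conclusion.** The rule is wrong as written, and the severity is minor. One year of age, 4 to under 5, has no assigned reporter on either PedsQL scale, and all four summarised scores are affected for any child in that band. These are counts of ages and scores; they do not measure an effect on results. How many enrolled children are in the band is not given and may be zero, and whether the summary will be produced is unknown. No test or decision depends on it.

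The gap itself rests on no assumption beyond the wording of items 4 and 5. That under 5 was meant is an inference from the protocol's bands, which is why the sponsor needs to confirm it.

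It would go too far to say that the SAP must also fix one reporter per child for the whole follow-up. A child aged about 4.5 to under 5 at baseline (5 − 0.5 = 4.5) turns 5 before Month 6, and the SAP does not say when age is taken. If age is taken at each visit, that child's change score could subtract a parent report from a self-report. If the baseline reporter is kept, the child may have only a self-report at Month 6, because protocol 3.7.4.2 lets the respondent depend on age, and the change score would be lost. The documents do not settle which is better, so this stays a question for the sponsor.

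**What to change.** In SAP 5.1.7.2, items 4 and 5, change the parent-report limit from under 4 years to under 5 years, with the sponsor confirming that this was the intent. The cost is one digit in two places; no new data are needed and no other analysis is affected.

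Separately, and only as a question, ask the sponsor to state whether age is taken at baseline or at each visit for children who turn 5 before Month 6. Either answer has a price: mixed reporters within a change score, or possibly a missing change score.

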5.2 Safety Analysis

Due to the early termination status, not all planned safety analyses will be provided due to lack of data. For an example, no subject received optional Tolvaptan treatment, the safety analyses specified in the SAP will not be applied to Optional Tolvaptan Treatment Component.

Safety variables to be analyzed include adverse events (AEs), clinical laboratory data, and vital signs. In general, summary statistics will be provided for safety variables based on all available data.

Baseline of the subjects receiving tolvaptan in the Optional Tolvaptan Treatment Component is the last evaluation prior to the first dose at each cycle in the Optional Tolvaptan Treatment Component. Baseline of the subjects participating in the Core Safety Follow-up Component is the last evaluations from the previous trial (tolvaptan in Trial 156-08-276), if the last evaluation was done in previous trials within one month of this trial starts. If more than one month passes between trials, the baseline will be the evaluations at the baseline visit of this trial.

Safety analyses by age categories (≥ 4 weeks to < 4 years, ≥ 4 years to < 8 years, ≥ 8 years to < 12 years, ≥ 12 years to < 18 years) will be provided. Safety analysis by underlying etiology (heart failure, hepatocellular disease, SIADH/other) will also be provided.

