3.1.1 Core Safety Follow-up Component

The core safety follow-up component of the trial is a 6-month period in which pediatric subjects (children and adolescents) with dilutional (euvolemic or hypervolemic) hyponatremia who previously participated in a tolvaptan hyponatremia trial will be followed (at a clinical trial site and/or through telephone calls), regardless of the need for treatment for hyponatremia, to assess the long-term safety of tolvaptan. There is no screening phase.

Enrollment into this trial should follow completion or discontinuation from the previous tolvaptan hyponatremia trial; the subject must have been off investigational medicinal product (IMP) for at least 7 days between trials. A longer lapse between completion of the previous tolvaptan hyponatremia trial and enrollment into this trial is permitted while enrollment is open.

The final laboratory assessments for liver function tests (LFTs) from the previous tolvaptan trial can serve as the baseline laboratory assessments for this trial if the values are within the normal range, and collected within 30 days of the baseline visit for this trial. However, LFTs for these subjects will be collected at Month 1 or Month 2 at a clinical site visit or local laboratory. If LFTs from the previous tolvaptan trial are abnormal, or collected > 30 days of the baseline visit of this trial, they will be assessed at baseline.

The last assessments in the previous tolvaptan trial will serve as the baseline assessments if collected within 30 days of enrollment into this trial. Otherwise, assessments will be repeated if > 30 days have lapsed since the previous tolvaptan trial.

Subjects enrolled in this trial will be assessed up to 7 times over the 6 month core safety follow-up component of the trial. The baseline and the Month 6/Early Termination (ET) visits are performed in the clinic, while assessments during Months 1, 2, 3, 4 and 5 will be conducted by telephone, unless LFTs are required at Month 1 or Month 2. During the in-clinic visits, subjects are evaluated for relevant trial information.

Baseline Visit

All subjects will attend the clinic for the baseline visit.

Months 1, 2, 3, 4 and 5

All subjects will receive telephone assessments for Months 1, 2, 3, 4, and 5. If LFTs are required at Month 1 or Month 2, the subject may obtain these results through a clinic visit or from a local laboratory.

Month 6/End of Trial Visit

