- 9) Body height and body weight will be measured.
- 10) Growth percentile will be calculated. Prior growth development information should also be collected, if available.

- 11) Tanner Staging will be transferred from the last assessments from the previous trial or completed as part of the physical examination, as appropriate. Historical staging information should also be collected, if available. A subject who has reached Stage 5 (both in pubic hair and genitalia) does not need to continue with Tanner Staging.
- 12) If the subject's last LFT (AST, ALT or BT) was abnormal or the subject's baseline visit occurred > 30 days after completion of the previous trial, the subject will be required to have LFTs assessed at baseline. If the subject's last LFTs were normal and the baseline visit occurred < 30 days after completion of the previous trial, LFTs will be collected at Month 1 or Month 2.
- 13) Quality of Life assessment will be performed, as appropriate by age and where available.
- 14) Concomitant medications will be recorded. If > 30 days have lapsed since the previous tolvaptan trial, medications taken within 30 days of enrollment will be recorded.
- 15) Adverse events will be assessed.

3.7.3.1.2 Months 1, 2, 3, 4, and 5

Subjects and/or their parents or legal guardians will be contacted by telephone at the end of Months 1, 2, 3, 4, and 5 (+ 2 weeks) to assess any new or ongoing AEs and to collect information on any medications administered since the last visit.

If the subject's last LFTs were normal and the baseline visit occurred < 30 days after completion of the previous trial, LFTs will be collected at Month 1 or Month 2 (in-clinic visit or local laboratory).

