5.4.1 Liver Transaminase Elevations

Management of abnormal liver function test results should be based on the investigator's clinical judgment. A liver function test result that is $2 \times$ ULN is generally accepted as a medically significant occurrence across various medical disciplines.

For a subject that experiences an elevation in AST or ALT that is $\geq 2 \times$ ULN or whose levels increase ≥ 2 times their initial baseline value in subjects with an elevated baseline value, a BT level should also be evaluated. If the BT is $\geq 2 \times$ ULN or ≥ 2 times their baseline value in subjects with an elevated baseline value, an IRE form with all values listed should be completed and also reported as an AE on the eCRFs.

The following guideline for repeat testing may be used by investigators as a reference for any subject with an ALT or AST $\geq 2 \times$ ULN:

- 1) ALT, AST, alkaline phosphatase, and BT should be repeated within 48 to 72 hours (needed to confirm abnormalities and determine if they are increasing or decreasing).
- 2) Inquiries should be made about symptoms (fatigue, nausea, vomiting, right upper quadrant pain or tenderness, fever, and/or rash) and signs like jaundice, yellowish discoloration of sclera, etc.
- 3) If discharged or transferred, the subjects should be retested locally and results given to the investigator immediately, along with that laboratory's normal ranges.
- 4) Close observation is required if symptoms persist or repeat testing shows ALT or AST $\geq 3 \times$ ULN for subjects with normal baseline measures OR 2-fold increases above baseline values for subjects with elevated values before drug exposure. If close monitoring is not possible, the drug should be interrupted until such monitoring is possible or the drug should be permanently discontinued.
- 5) All trial subjects with evidence of possible DILI should be followed until all abnormalities return to normal or to the baseline state.

Close observation may involve:

- 1) Repeating liver enzymes and serum bilirubin tests 2 or 3 times weekly.
- 2) Frequency of retesting can decrease to once a week or less if abnormalities stabilize or if the trial drug has been interrupted/discontinued and the subject is asymptomatic.
- 3) Obtaining a more detailed history of symptoms and prior or concurrent diseases.

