The final laboratory assessments for liver function tests (LFTs) from the previous tolvaptan trial can serve as the baseline laboratory assessments for this trial if the values are within the normal range, and collected within 30 days of the baseline visit for this trial. However, LFTs for these subjects will be collected at Month 1 or Month 2 at a clinical site visit or local laboratory. If LFTs from the previous tolvaptan trial are abnormal, or collected > 30 days of the baseline visit of this trial, they will be assessed at baseline.

The last assessments in the previous tolvaptan trial will serve as the baseline assessments if collected within 30 days of enrollment into this trial. Otherwise, assessments will be repeated if > 30 days have lapsed since the previous tolvaptan trial.

Subjects enrolled in this trial will be assessed up to 7 times over the 6-month core safety follow-up component of the trial. The baseline and the Month 6/Early Termination (ET) visits are performed in the clinic, while assessments during Months 1, 2, 3, 4 and 5 will be conducted by telephone, unless LFTs are required at Month 1 or Month 2. During the in-clinic visits, subjects are evaluated for relevant trial information.

Baseline Visit

All subjects will attend the clinic for the baseline visit.

Months 1, 2, 3, 4 and 5

All subjects will receive telephone assessments for Months 1, 2, 3, 4, and 5. If LFTs are required at Month 1 or Month 2, the subject may obtain these results through a clinic visit or from a local laboratory.

Month 6/End of Trial Visit

All subjects will attend the clinic for the Month 6/End of Trial visit.

Optional Tolvaptan Treatment Component

Subjects enrolled in the 6-month core safety follow-up component may be eligible to receive optional tolvaptan treatment for their hyponatremia. Eligibility for optional tolvaptan treatment must be determined at the pre-treatment baseline visit (Day -4 to Day 1) of each dosing cycle. Eligible subjects can be treated at any time with optional

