5.2.3 Laboratory Test Results

Summary statistics for the clinical laboratory measurements at baseline and post-baseline visits, and summary statistics of changes from baseline to each visit will be presented. Shift tables will be produced, assessing low-normal-high (at baseline) to low-normal-high (at post-baseline visit).

The incidence of potentially clinically significant abnormal lab results will also be summarized. Listings of potentially clinically significant abnormalities will also be provided.

According to FDA (Food and Drug Administration) Guidance,¹ laboratory measurements that signal the potential for drug-induced liver injury (DILI) will be reported. An incidence table and a listing will be provided for subjects who meet one or combinations of the following criteria:

- 1) ALT (alanine transaminase) or AST (aspartate transaminase) $\geq 3x$ upper limit of normal (ULN) (or baseline value for subjects with abnormal baseline)
- 2) Increase in bilirubin $\geq 2x$ ULN (or baseline value for subjects with abnormal baseline)

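### SAP 5.2 sets the core LFT baseline on timing alone, against SAP Section 3 and protocol 3.1.1, so the change and shift tables differ and, under some readings of SAP 5.2.3, the DILI flag can differ

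*SAP*

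**What the plan says.** SAP 5.2 states its scope: "Safety variables to be analyzed include adverse events (AEs), clinical laboratory data, and vital signs". For core subjects the baseline "is the last evaluations from the previous trial (tolvaptan in Trial 156-08-276), if the last evaluation was done in previous trials within one month" before entry. The baseline-visit value is used only when more than one month has passed.

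SAP Section 3 and protocol 3.1.1 contain a similar general timing rule, but both add a rule for liver function tests (LFTs). Previous-trial LFTs "can serve as the baseline laboratory assessments for this trial if the values are within the normal range" and were taken within 30 days. SAP Section 3 continues: "If LFTs from the previous tolvaptan trial are abnormal, or collected > 30 days of the baseline visit of this trial", they are measured at baseline. Protocol 3.7.3.1.1 makes this a visit requirement: if the last LFT was abnormal or the gap exceeds 30 days, "the subject will be required to have LFTs assessed at baseline".

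SAP 5.2.3 flags potential drug-induced liver injury (DILI) at ALT or AST ≥ 3× "upper limit of normal (ULN) (or baseline value for subjects with abnormal baseline"). The second criterion is "Increase in bilirubin" ≥ 2× ULN, with the same parenthetical.

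No subject received optional tolvaptan (SAP 5.1 and 5.2), so only the core baseline applies.

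**The concern.** A programmer has two incompatible baselines for any child whose last LFT in the previous trial was abnormal and recent. Post-treatment safety is the aim of the core component, and that component is all that will be analysed. Hepatocellular disease is one of the planned etiology strata, so abnormal entry LFTs are foreseeable. The DILI table is the only planned output with stated ULN multiples; SAP 5.2.3 gives no limits for its potentially clinically significant listings. If the abnormal older value stays as baseline after the child has normalised, a later rise could be judged against the wrong reference.

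**Working it through.** The plan gives no figure to reproduce. All values below are assumed, in multiples of ULN, with a value at or below 1.0 taken as normal. Let p = last previous-trial value (abnormal, recent), v = baseline-visit re-test, x = later value, and b = whichever of p or v is the baseline.

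**Step 1: which LFTs exist for this child.** The Month 1 or 2 LFT is scheduled only when the last LFT was normal and recent (protocol 3.7.3.1.1, 3.7.3.1.2). The Month 6 list (3.7.3.1.3) has none. Protocol 3.7.5.2 allows others only for AE follow-up. So v is the only scheduled core LFT, and any x must be AE-driven or unscheduled.

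**Step 2: change and shift tables.** Take p = 2.5, v = 1.0.
- SAP 5.2: baseline 2.5, post-baseline 1.0, change 1.0 − 2.5 = −1.5, shift from high to normal.
- Section 3: baseline 1.0, with no scheduled post-baseline value, so no change or shift.

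This difference does not depend on how SAP 5.2.3 is read.

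**Step 3: ALT/AST flag.** The parenthetical in SAP 5.2.3 can be read three ways when b > 1:
- Replacement: x ≥ 3b takes the place of x ≥ 3.
- Additional: x ≥ 3 or x ≥ 3b. Since b > 1 gives 3b > 3, the threshold is min(3, 3b) = 3.
- Literal: x ≥ b.

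When b ≤ 1, all three give x ≥ 3.

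| Case | Reading | Threshold, SAP 5.2 (b = p) | Threshold, Section 3 (b = v) | Result |
|---|---|---|---|---|
| A: p = 2.5, v = 1.0, x = 4.0 | Replacement | 3 × 2.5 = 7.5 | 3.0 | missed / caught |
| A | Additional | 3.0 | 3.0 | caught by both |
| A | Literal | 2.5 | 3.0 | caught by both |
| B: p = 1.5, v = 2.5, x = 5.0 | Replacement | 3 × 1.5 = 4.5 | 3 × 2.5 = 7.5 | caught / missed |
| B | Additional | 3.0 | 3.0 | caught by both |
| B | Literal | 1.5 | 2.5 | caught by both |

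Under replacement, the flags differ only when x lies between 3 × max(1, p) and 3 × max(1, v): from 3.0 to below 7.5 in case A, and from 4.5 to below 7.5 in case B. Under the literal reading, case A differs only from 2.5 to below 3.0. Under the additional reading they never differ.

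**Step 4: the wording matters even with one agreed baseline.** At b = 2.0 and x = 4.0, replacement gives a threshold of 3 × 2.0 = 6.0 (not flagged), additional gives 3.0 (flagged) and literal gives 2.0 (flagged).

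**Step 5: bilirubin.** SAP 5.2.3 does not say whether the increase is a level or a change. At b = 1.5 the flag could fall at:
- 2.0 (level, ULN kept)
- 2 × 1.5 = 3.0 (level, baseline)
- 1.5 + 2.0 = 3.5 (rise of 2× ULN)
- 1.5 + 3.0 = 4.5 (rise of 2× baseline)

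Read as a rise, the flag depends on the baseline even if ULN is kept: p = 1.5 gives 1.5 + 2.0 = 3.5, while v = 0.8 gives 0.8 + 2.0 = 2.8.

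**Step 6: changing the baseline alone is not enough.** With p = 1.5 and v = 4.0, the replacement threshold moves from 3 × 1.5 = 4.5 to 3 × 4.0 = 12.0. The re-test of 4.0 is missed either way.

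**The case against.** The general timing sentence in Section 3 might seem to support SAP 5.2. It does not for LFTs, because both documents add a specific rule that an abnormal value fails.

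Stronger objections concern size, and most of them stand. The flag effect is conditional on the reading. It needs a later LFT that is not scheduled, and the value must fall in a particular band. The trial ended early, and SAP 5.2 already says not all safety analyses will be produced. By-visit summaries, AE tables and the potentially clinically significant listings remain. A baseline-relative threshold is also a recognisable choice where chronic liver disease is a stratum.

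There is a case for the SAP 5.2 rule too: the previous value and the re-test are the only scheduled pair for such a child, and using the re-test as baseline removes the change between them. That is a real cost, but it does not resolve the contradiction.

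Two stronger inferences are tempting. A reader might infer that every child with an abnormal recent LFT gets a different DILI flag; Step 3 shows that this does not follow. A reader might also infer that the SAP multiple contradicts protocol 5.4.1, whose close-observation item uses 3× ULN "for subjects with normal baseline measures OR 2-fold increases above baseline values for subjects with elevated values before drug exposure". The documents do not establish an error there. That item belongs to an optional reference for investigators, and a reporting table need not match a monitoring trigger. Its two-fold increase could also mean 2b or, as a change, b + 2b = 3b.

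**Conclusion.** The contradiction over the LFT baseline is clear from the text, and it changes the change-from-baseline and shift tables for any core child with an abnormal recent LFT. The DILI flag can differ in either direction. For ALT/AST this is limited to the replacement or literal reading and to values in the bands shown. The missed value of 4.0× ULN in case A arises under the replacement reading only. Separately, the wording of SAP 5.2.3 does not fix the flag.

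Severity is minor. The documents do not give the number of children affected, and it is likely to be small. The conclusion assumes that the visit lists match the grid of Table 3.7.1-1, and that any AE-driven LFTs reach the database. The difference in wording between the SAP multiple and the protocol 5.4.1 multiples is a note for the sponsor to check, not an error.

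**What to change.** Make both changes together.

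1. **SAP 5.2:** use a previous-trial LFT as baseline only if it is normal and within 30 days; otherwise use the baseline-visit value.
2. **SAP 5.2.3:** show ALT/AST ≥ 3× ULN, bilirubin ≥ 2× ULN and their combination for every core child, counting baseline-visit, repeat and unscheduled values. Put the baseline-relative criterion in a separate row as an explicit inequality, and state whether the bilirubin increase is a level or a change. The ULN rows then depend on neither the baseline chosen nor the replace-or-add reading.

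The cost is SAP wording and a few table rows; SAP 5.2.4 already brings repeats and unscheduled values into outlier analyses. Whether AE-driven LFTs are in the database must be confirmed. A few more cases will be listed among children with chronic liver disease. A child whose re-test becomes the baseline may have no scheduled post-baseline LFT for the change and shift tables, so list the previous-trial value beside the re-test.
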